7.1 Statistical Analysis

The study statistician will prepare a full statistical analysis plan prior to data analysis, which will be agreed with the PSC.

[figure not shown]
Although the exact details of the analysis will be in that plan, the broad analysis will be as follows. Analysis of the primary outcome will use analysis of covariance to undertake a between-group comparison adjusting for clustering by service and pre-specified covariates to estimate the effect of our intervention on outcomes, for those patients referred to IAPT telephone-treatment.

Robustness check: The focus of our intervention will be on improving patient outcomes and engagement among those offered telephone treatments. However, there is a risk that our intervention will affect the types of patients who are offered telephone treatment in intervention sites, compared to controls. We will conduct a range of robustness checks to assess any potential impact, and these will be fully detailed in the statistical analysis plan. These checks will include: exploring interview data with professionals to understand changes that might have been implemented; comparison of types of patients referred for telephone-treatment before and after the intervention; comparing baseline characteristics of patients in intervention and control groups. If we identify bias related to changes in referral practice, we will undertake sensitivity analyses to test the robustness of the primary analysis. Sensitivity analyses will include adding control for unbalanced covariates into the primary analysis, and re-analysing using patient-level propensity score adjustment or using a difference-in-difference method.

Economic evaluation

The study economist will prepare a full economic analysis plan prior to data analysis, which will be agreed with the PSC.

Although the exact details of the analysis will be in that plan, the broad analysis will be as follows. We will assess the intervention's cost-effectiveness at two levels. The first (within-study analysis) will assess whether the intervention is cost-effective in the services and participants included in the implementation trial. The second (decision analysis) will explore potential cost-effectiveness outside the trial setting. Both analyses will use a cost-effectiveness acceptability approach to generate a cost-effectiveness acceptability curve, estimate the likelihood that the intervention is cost-effective, and calculate the net benefit statistic [Briggs & O'Brien 2001; Fenwick et al 2001; Hoch et al 2002; Pedram Sendi & Briggs 2001].

Within-study analysis: The primary analysis will use the NHS and Personal Social Services Perspective, (recommended by NICE) and time horizon of 6-months from 6-month follow-up to end of scheduled follow up (12-months). Regression analysis with bootstrapping, controlling for key covariates will estimate the net costs and QALYs of the intervention and generate a cost-effectiveness acceptability curve [Briggs and O'Brien 2001; Fenwick et al 2001; Hoch et al 2002; Pedram et al 2001], estimate the likelihood the intervention is cost-effective at a willingness to pay threshold of £15,000, and the net benefit statistic.

We will combine psuedonymised, routine IAPT data with the EQ-5D-5L [Herdman et al 2011] and health and social care service use data collected from participants at 6 and 12-month follow-up. The Economic Patient Questionnaire (EPQ) used in the NIHR funded EQUIP programme will be adapted to collect data about use of non-IAPT services (e.g. hospital, CMHT, primary care, social services and third-sector care). Questions about non-NHS & social care services paid for by the participant and paid/unpaid employment will be included for sensitivity analysis.

Costs will be estimated as service use multiplied by published unit cost, by type of service [PSSRU 2017, Department of Health 2017]. Intervention costs will include the costs of providing the intervention and annual equivalent cost developing intervention components. QALYs will be estimated from EQ-5D-5L responses and published utility-tariffs [van Hout et al 2012; Devlin et al 2018].

The primary analysis will use the utility-tariff recommended by NICE at the time of the analysis. All missing data will be treated as missing at random. Multiple imputation will use predictive mean matching and sequential chained equations. Cost data will be imputed by category so that all available data inform imputed values. Sub-group analyses will be defined prior to primary analysis, based on research team and Steering Committee.

It is anticipated a combined decision-tree and Markov model will be used to represent immediate treatment pathways in the index episode (decision tree) and the longer-term course of depression and anxiety (Markov model). The analysis will take an NHS and social care perspective to explore cost-effectiveness over longer time-frames (5 and 10 years) and to explore potential for the intervention to be cost-effective in IAPT services and patients not included in the trial.

Qualitative Analysis

Analysis will occur blind to trial outcomes to avoid biased interpretation [Oakley et al 2006]. Anonymised transcripts will be analysed independently by two qualitative researchers using thematic analysis, guided by the constructs of NPT and CFIR.

Analysis will be supported by NVivo software [QSR International Pty Ltd 2018]. Individuals will meet regularly to discuss codes, develop a provisional coding framework

and ensure that all emerging codes remain grounded in the original data. Additional members of the research team may assist with this.

7.2 Sample Size:

Enriched Sample

There are approximately 107 IAPT providers in England. We will recruit a minimum of 22 services. With 11 clusters per arm, an ICC of 0.027, a baseline-endpoint correlation of 0.5 and 100 patients/site, we would have 85% power to detect a standardised mean difference of 0.2. This calculation is based on a mean cluster size of 607 (based on the routine data per site) and a co-efficient variation of 1.14 (due to the high variation in siite size). As expected with a relatively small number of clusters, this calculation is sensitive to ICC; we retain 70% power at an ICC of 0.04.

Workshops

Professional attendance at workshops will vary depended on service size and professional availability to attend. We anticipate approximately 10-20 professionals per site (total 130-260 participants).

Telephone training

Professional attendance at the training sessions will vary depending on service size and professional ability to attend. We anticipate approximately 5-20 practitioners per site (total 65-260).

[figure not shown]
Qualitative Interview Sample

Patients

We will recruit until data saturation [Miles and Huberman 1994] with an estimated sample size of 25-30 patients from intervention arm sites who have accessed telephone treatment following implementation of the EQUITy intervention.

Professionals

We will recruit until data saturation [Miles and Huberman 1994], with an estimated sample size of 25-30 professionals (Service Leads, Managers, Supervisors, PWPs) from intervention arm sites.

The total sample size across all workshop, training sessions and studies will be 3180 (minimum 2845).

9) DATA MONITORING AND QUALITY ASSURANCE

The study will be subject to the audit and monitoring regime of The University of Manchester. Programme Steering Committee (PSC) comprising an independent chair, statistician, key IAPT professionals and PPI expert will convene and meet twice-yearly.

10) SAFETY CONSIDERATIONS AND ADVERSE EVENTS

Given the nature of the study and methodology that will be adopted we anticipate no clear risks inherent in the intervention under evaluation that would make us set a priori stopping criteria.

If any untoward event is observed, any decision about stopping the trial (including in response to data generated outside the trial) will follow regulatory procedures.

II) PEER REVIEW

The study was reviewed extensively by external reviewers and a Panel as part of the NIHR PGfAR application process. The statistical aspects of the research were reviewed by [name], Professor of Medical Statistics & Trials Methodology, Kings College London. In addition, during the NIHR application process it was reviewed anonymously by external reviewers.

12) ETHICAL and REGULATORY CONSIDERATIONS

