5.2 Study Intervention and Procedures

STUDY DESIGN

The overall design is a cluster randomised trial comparing IAPT services receiving the EQUITy intervention with usual IAPT services. We will include an internal pilot (over 6 months).

A linked process evaluation will be conducted using qualitative methods with patients and professionals (and is described in a separate section for clarity).

[figure not shown]

Description of intervention

The EQUITy intervention is a service quality improvement intervention which seeks to build on existing services and does not involve the introduction of a new treatment.

The intervention is made up of 3 components (see Box 3):

- 1. Guidelines for services, team workshop and follow-up meetings
- 2. Practitioner telephone training
- 3. Resources for patients

Box 3 Summary of the EQUITy intervention

The intervention consists of three components:

- 1. Guidelines for services, team workshop and follow-up meetings
- 2. Practitioner telephone training
- 3. Resources for patients

Guidelines for services, team workshop and follow-up meetings

Whole team day workshop with afternoon team action planning task.

The service guidelines were developed as a result of previous EQUITy studies (detailed in Box I). They have been refined following feedback from stakeholders in the feasibility study. The guidelines cover 5 areas: I) Promoting Telephone Work 2) Key elements of Telephone -Work 3) Working Environment and Resources 4) Boosting Telephone Skills and 5) Promoting Reflection.

Team Workshop (full-day). The workshop will provide information about: I-The EQUTy research programme, 2-The EQUITy intervention and 3-Policy and Evidence for psychological interventions delivered by telephone; and it will introduce the Service Guidelines Booklet and facilitate its implementation in routine practice.

Follow-up meetings (45-60 minutes, within 6-8 weeks of workshop/training) 6-8 weeks following the team workshop a follow-up session (online or via telephone) will take place. During this session general thoughts and feelings related to the implementation of the EQUITy intervention will be explored, a review of proposed action plans will take place and next steps will be identified and discussed. The named action plan lead within each site will be expected to attend, with other team members who attended the workshop/training also invited.

[figure not shown]

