|----------------|-------------------------|--|---|--|---|---------------|
| Eligible sites | | training outcomes | INTERVENTION DELIVERY | Professional post- workshop outcomes | Professional qualitative interviews | |
| | Control cluster | Intervention cluster | Patients entering the service Routine data (Baseline-last treatment session) | | Enriched data 6mth outcomes | Enriched data |

USUAL CARE

Patients entering the service

The following table (Table I) provides an overview of trial activities and timelines for the EQUITy trial, most of which relate to the intervention arm. Further information about the enriched patient sample follows the table.

Table I

| ENTRY INTO | I-day service guidelines team | |
|---------------|--|---|
| Week I | workshop (PWPs, service leads, admin staff etc) | |
| Weeks 2 – 3 | Practitioner telephone training Two 3-hour training sessions held on separate days | Weeks 2 - 24 Distribution of patient resources (electronic |
| Weeks 6 – 8 | 45-60-minute action plan lead/team follow-up meeting online or via telephone | and/or hard copies dependent on service preference) |
| Weeks 10 - 24 | Offer of additional follow-up meetings online or via telephone | Weeks 3 - 24 |
| Weeks 16 – 24 | Qualitative interviews/discussion groups with patients and professionals | Recruitment of an enriched patient sample (intervention and control arms) |

Sites will be informed of their allocation approximately I month prior to their chosen intervention dates (Trial Entry Date). Regardless of the trial arm they are allocated to, the Trial Start Date for each service will be the date of their chosen workshop (the initial delivered component of the intervention).

EVALUATION

The trial design is embedded in routine IAPT services and takes advantage of data that is available through IAPT operations, supplemented by bespoke research data. IAPT datasets are comprehensive at baseline with consequent high external validity [Gyani et al 2011]. However, they lack long term outcomes, as services do not follow up service users after discharge. Additionally, they do not collect broader service use measures and generic, preference-based health status measures.

In order to effectively and efficiently evaluate the long term and economic impact of the EQUITy intervention, we will combine routine IAPT data with additional data from consenting patients from the intervention and control sites (see Figure 1).

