| Additional Information | | | | |
| IAPT Employment Status questionnaire | X | | | |
| Patient Assessment Experience | X | | | |
| Questionnaire | | | | |
| Patient Treatment Experience | | X | | |
| Questionnaire | | | | |
| Number of sessions attended | | X | | |
| Intervention Arm only | • | • | . | • |
| PWP who delivered telephone sessions | | X | | |
| Additional participation | | | | |
| Qualitative interview | | X | | |

X = Data collected routinely by services; X = Data collected by the research team; * = Collection of this measure is dependent on the patient's presentation

Practitioners who are involved in the intervention arm sites will be asked to complete before and after workshop and training measures to explore impact and acceptability of the EQUITy intervention. They will also be invited to take part in a qualitative interview. Practitioners who are working in a site allocated to the control arm will not be asked to take part in any data collection or feedback activities.

Table 3. Schedule of enrolment and data collection for professional data (intervention and control arms).

[figure not shown]
| | Study Per | Study Period | | |
|---------------------------|--------------|---------------|--|--|
| | Pre-activity | Post-activity | | |
| Intervention Arm Activity | • | • | | |
| Team Workshop | | | | |
| Demographic questionnaire | X | | | |

| COM-B | X | X |
|----------------------------|---|---|
| ORIC | X | |
| | | |
| | | |
| Telephone Training | | |
| Demographic questionnaire* | Х | |
| COM-B | X | X |
| TARS | | X |

^{*} if they have already completed this at the first team workshop, they will not be asked to complete this again.

STUDY PARTICIPANTS

6.1 Inclusion Criteria:

Services

Any IAPT service (NHS or third sector) who supports patients at Step 2 over the telephone will be eligible. Services will need to be providing at least 20% of their treatment sessions using the telephone and have enough referrals likely to allow for a sample of 100 patients for the enriched sample (aim to achieve 100 but not a compulsory condition of involvement).

Multiple IAPT services within the same Trust will be included if they work independently to each other.

Patients

Patients - Routine IAPT dataset

[figure not shown]
We will request pseudonymous IAPT routine data of all patients who access the service, irrespective of which treatment modality they are referred to (12 months of data pre-intervention implementation).

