We are interested in exploring the data associated with patients accessing Step 2 treatment, which may include information of if they have been stepped up to receive Step 3 treatment. Some services may not be able to manually extract only the data requested by the research team from the dataset that they submit regularly to NHS England and thus they will be unable to exclude any subsequent Step 3 service data in the dataset they provide. This is due to resource and time issues. They will, however, be able to remove any patient identifiers such as full date of birth and postcode, ensuring that the date set remains pseudonymous. If this occurs the research team will manually remove any irrelevant Step 3 data. The data that they submit to NHS England is made available in the public realm thus no concerns have been identified about the sharing of this data.

Patients – enriched sample

As a pragmatic trial of a model of a service quality improvement intervention, the inclusion criteria are simple to enhance the external validity of the study. All adults (18+) accessing telephone-delivered Step 2 treatment following randomisation (intervention or control arm) will be eligible to participate in the enriched sample.

All patients who enter a service and are referred to telephone treatment will be invited to consent to being part of enriched data sample (although we will restrict the numbers in

that sample in each site). Recruitment will continue for a maximum of 9 months at each site to allow for as close to 100 patients consenting to participate.

Patients – post-intervention implementation qualitative interviews

We will purposively sample across all the services allocated to receive the EQUITy intervention (i.e. 11) to ensure variance in clinical and organisational contexts. A sampling frame will capture patients with different clinical profiles (diagnosis, severity) and levels of intervention engagement (e.g. no sessions attended, first session only, multiple sessions) Maximum variation sampling will ensure patients of different socio-economic background, age, ethnicity and gender are included.

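### The primary comparison is among patients referred to telephone treatment after services know their arm, yet the sensitivity analyses for changed referral run only if bias is first identified

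*Protocol*

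**What the plan says.** Section 7.1 describes the primary analysis as an ANCOVA, adjusted for clustering by service and for pre-specified covariates, "to estimate the effect of our intervention on outcomes, for those patients referred to IAPT telephone-treatment". Randomisation is of services (6.4). Patients arrive afterwards. For the enriched sample, "All adults (18+) accessing telephone-delivered Step 2 treatment following randomisation (intervention or control arm) will be eligible" (6.1), and "Sites will be informed of their allocation approximately I month prior to their chosen intervention dates" (5.2, below Table 1).

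The robustness paragraph of 7.1 then acknowledges that "there is a risk that our intervention will affect the types of patients who are offered telephone treatment in intervention sites". It commits, without condition, to three checks: interviews with professionals, a comparison of referred patients before and after the intervention, and a comparison of baseline characteristics between arms. What follows is conditional: "If we identify bias related to changes in referral practice, we will undertake sensitivity analyses to test the robustness of the primary analysis". The analyses named are adding unbalanced covariates to the primary model, and "re-analysing using patient-level propensity score adjustment or using a difference-in-difference method". Full detail of the checks is left to the SAP.

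Three other places bear on how likely a referral shift is. On the service guidelines, Box 3 says: "The guidelines cover 5 areas: I) Promoting Telephone Work". The opening of the Outcome Measures section lists uptake of telephone treatment among the programme's aims. Against these, 6.3 says that decisions about a patient's treatment are not directly affected.

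On data, 6.1 requests routine records of all patients "irrespective of which treatment modality they are referred to", and 5.2 requests them for 12 months before and 12 months after implementation.

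**The concern.** Randomising services protects a comparison of everyone who enters them. It does not protect a comparison of a subgroup formed later by a referral decision, if the intervention can move that decision. If intervention services send a different mix of patients to telephone treatment, the difference in case mix becomes part of the estimated effect. It could imitate a benefit or hide one.

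The protocol sees this risk, but its response waits for detection. Measured characteristics can look balanced while motivation, complexity or preference for telephone contact differ. In that case the checks find nothing, the sensitivity analyses are not triggered, and the primary estimate is reported without them. Of the analyses named, covariate and propensity adjustment deal only with measured differences. Difference-in-difference among telephone-referred patients removes stable differences between sites, but not a change in case mix that the intervention itself produces. No analysis named in 7.1 avoids conditioning on referral to telephone.

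**Working it through.** **1. Reading the sections together**

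- Unit randomised: the service (6.4).
- Unit analysed: the patient referred to telephone treatment (7.1).
- Order: the service knows its arm about a month before its trial start date (5.2); patients then enter and are referred.
- Can the intervention move the referral? 7.1 says it may. Box 3 and the uptake aim make it plausible. 6.3 rules out direct influence only.

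**2. What the checks can see**

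- Before/after and between-arm comparisons show recorded characteristics only.
- Professional interviews come from intervention sites only. The text before Table 3 exempts control-arm practitioners from data collection, and 6.1 samples interviewees from services receiving the intervention.

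**3. Precision of the design (7.2)**

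Inputs: k = 11 clusters per arm, ICC 0.027, baseline correlation r = 0.5, mean cluster size m = 607, CV = 1.14, target 0.2 SD. Two-sided alpha of 0.05 is assumed, because 7.2 does not state it.

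- L = m·ICC/(m·ICC + 1 − ICC) = 16.389/17.362 = 0.944
- Relative efficiency for unequal clusters = 1 − CV²·L(1 − L) = 0.931
- Effective n per arm = k·m·0.931/{[1 + (m − 1)·ICC](1 − r²)} = 11 × 607 × 0.931/(17.362 × 0.75) ≈ 477
- SE = √(2/477) ≈ 0.065 SD
- Power, non-central t with 20 df: 83.6%, against the plan's 85%. At ICC 0.04 it is 69.4%, against 70%.

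The stated power therefore reproduces within 2 percentage points, and 0.065 SD is a fair SE for the next step. With 100 patients in every site the SE would be 0.071 SD.

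**4. Illustrative bias**

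Let s be the share of the intervention arm's telephone patients who are there only because referral changed, and g their difference in adjusted outcome from the rest, in SD. With no true effect, the intervention mean moves from μ to (1 − s)μ + s(μ + g) = μ + s·g, so the bias is s·g. Both s and g are assumptions.

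| s | g = 0.1 | g = 0.2 | g = 0.3 | g = 0.5 |
|---|---|---|---|---|
| 5% | 0.005 | 0.010 | 0.015 | 0.025 |
| 10% | 0.010 | 0.020 | 0.030 | 0.050 |
| 20% | 0.020 | 0.040 | 0.060 | 0.100 |
| 30% | 0.030 | 0.060 | 0.090 | 0.150 |

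Against 0.2 SD this runs from 0.005/0.2 = 2.5% to 0.15/0.2 = 75%. For scale, if the telephone share rose from p0 to p1 purely by adding patients, s = (p1 − p0)/p1. A rise from 50% to 60% (assumed) gives 0.10/0.60 = 17%.

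With SE 0.065 and 20 df, the chance of a significant result when the true effect is zero is:

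| Bias (SD) | Error rate |
|---|---|
| 0.02 | 6% |
| 0.04 | 9% |
| 0.06 | 14% |
| 0.10 | 31% |

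With SE 0.071 and a normal approximation the figures are 6%, 9%, 14% and 29%.

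**5. If detection meant a significance test**

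The protocol does not say that it does. Taking the same ICC for a baseline variable, with no baseline adjustment, power to detect a 0.1 SD shift between arms is about 25-27% at m = 607 and CV 1.14, and 21-23% at 100 per site. A trigger of that kind would usually stay silent.

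**The case against.** The strongest reply is that the protocol names this risk, promises three checks without condition, and defers detail to an SAP that is not at hand. One of those checks, the before/after comparison of referred patients, looks at referral change directly, and the pre-period data exist for it. Its lists of checks and sensitivity analyses are open-ended. The primary model adjusts for covariates, which absorbs part of any measured shift. Section 5.1 says telephone use is already substantial since the pandemic, which may limit further change. All of this stands, and it keeps the point modest.

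A reader might infer four stronger things that the document does not support.

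- That the intervention is meant to change who is referred. Section 7.1 calls this a risk and places the focus on those offered telephone treatment, 6.3 denies direct influence, and the content of the first guideline area is not shown. The text supports only that referral may change.
- That a detect-then-adjust rule biases the primary result. The primary ANCOVA is fixed and is reported whatever the checks show; the conditional models only test its robustness.
- That no analysis irrespective of modality is planned at all. The protocol names none, but the SAP could contain one.
- That a serious bias is likely. No figure in the protocol speaks to its size.

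What the reply does not answer is the condition itself. It is a rule fixed in the protocol, and it makes the safeguard depend on checks that cannot see unmeasured selection.

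**Conclusion.** The point holds as a proportionate improvement to a rule that the protocol states. The primary population is formed after services know their arm, the protocol accepts that the intervention may alter it, and the sensitivity analyses should not wait for bias to be found. The illustrative 0.005-0.15 SD rests wholly on the assumed s and g and on the remaining patients having the same mix in both arms; the low end is negligible and the high end is most of the target effect. The documents do not show where in that range the trial would fall, and this is the reason to run the analyses regardless. The stated power is not in dispute here.

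**What to change.** In the sentence of 7.1 that reads "If we identify bias related to changes in referral practice, we will undertake sensitivity analyses to test the robustness of the primary analysis", delete the opening conditional clause and state that the listed sensitivity analyses will be run whatever the checks show. Then add:

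1. A supportive cluster-adjusted ANCOVA of end-of-treatment PHQ-9 and GAD-7 on all patients entering each service in the 12-month post period, irrespective of modality, with all Step 2 patients as a secondary set. Step 2 placement also follows allocation, so all entrants is the cleaner set.
2. A between-arm comparison of the pre-to-post change in the share referred to telephone and in the case mix of those referred.

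State two limits. Analysis 1 applies to end-of-treatment outcomes only, because the 6- and 12-month data come from telephone patients. Difference-in-difference among telephone-referred patients removes stable site differences, but not case-mix change caused by the intervention. Use the results to interpret the primary estimate, with no rule that they must agree in direction.

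The cost is wording and a few extra models on routine data already requested. Two practical points need confirming. The parenthesis in 6.1 mentions only the pre-period while 5.2 covers both periods, so the post-period request should be confirmed as covering all modalities. Section 6.1 also plans to remove Step 3 records judged irrelevant, and the all-entrants set would need them kept where services supply them.

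The statistical downside is dilution. If half of entrants used the telephone and only they benefited (assumed), a 0.2 SD effect would appear as 0.5 × 0.2 = 0.10 SD. The all-entrants analysis therefore supports the primary analysis and does not replace it.
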